# 8.2.3 Period 3 (Cohort 1 and Cohort 2) - Outpatient Dosing

Period 3 will include a titration phase of approximately 12 weeks and a maintenance phase of approximately 12 weeks for a total outpatient exposure to CLTX-305 (encaleret) of approximately 24 weeks. In Period 3, the initial outpatient dose of CLTX-305 (encaleret) will be based on the results from inpatient Periods 1 and 2. Outpatient titration will be conducted by the NIH investigators with the goal of optimizing the CLTX-305 (encaleret) dose without calcitriol, targeting normal cCa and phosphorus concentrations while minimizing the need for calcium supplements, avoiding symptoms of hypo- or hypercalcemia, and minimizing the extent of hypercalciuria. If blood cCa levels are > 10.5 mg/dL, the NIH investigators can consider holding the CLTX-305 (encaleret) dose and restarting CLTX-305 (encaleret) at a lower dose after blood cCa has decreased to < 10 mg/dL. Oral calcium supplementation may be used as needed on top of a minimum dietary intake of at least 1000 mg daily. Participants previously treated with magnesium and potassium citrate supplements when not on CLTX-305 (encaleret) may not be restarted on treatment during Period 3, if the blood magnesium and urine citrate are within the normal ranges during Period 2.

For participants who require CLTX-305 (encaleret) doses < 10 mg BID to achieve the treatment goals described above, and the 5 mg tablets are not available, the 10 mg tablets may be split according to the related specifications indicated in the Pharmacy manual provided by the Sponsor in order to receive 5 mg BID dosing. Of note, no other dose strength besides the 10 mg tablet may be split. If the 10 mg tablet needs to be split, the participant should cut one 10 mg encaleret tablet each day and take half of the tablet in the morning and the other half of the split tablet in the evening, assuring that the participant receives a full 10 mg dose per day. Participant should follow the manufacturer instructions for use included with the pill cutter. In the event that half of the split 10 mg tablet is lost, the participant should cut a new tablet in half for the evening dose and discard the remaining half. The participant should start with a new 10 mg tablet the following morning.

Study visits include inpatient NIH Clinical Center visits every 8 weeks. PK assessments will be done at week 24 only; PD assessment will be done at weeks 8, 16 and 24 for evaluation of safety. AEs and concomitant medications will be recorded during these visits. Participants will be contacted by telephone per protocol at intervals during titration and maintenance, to

review the results of outpatient laboratory blood and urine assessments, confirm adequacy of the current regimen of study medication (including supplements), inquire about hypo/hypercalcemia symptoms, and assess for AEs. Participants are considered to have completed the study once they complete 24 weeks of Period 3 and the safety follow-up visit.

For details on the visit schedule and assessments in Period 3 see Section 1.3.

The total blood volume collected over 24 weeks during Period 3 for each participant will be less than the blood volume limits per participant as per NIH Guidelines for Blood Draw Limits for Research Purposes (M95-9, June 2009). This includes the 3 inpatient NIH visits.

If a participant reaches week 24 prior to the LTE being in place, the participant can discontinue CLTX-305 (encaleret) and restart calcitriol and/or calcium supplements until the LTE is implemented. Upon entry into the LTE, the participant will be reconsented to and may restart CLTX-305 (encaleret) at the previous therapeutic dose determined in Period 3.

# 8.2.4 Long-term Extension (LTE)

LTE will include continuation of outpatient treatment with CLTX-305 (encaleret) at the dose established in the maintenance phase of Period 3. CLTX-305 (encaleret) doses may be titrated as needed during LTE based on assessment of both blood and urine calcium results as described, with the goal maintaining optimal CLTX-305 (encaleret) dose without calcitriol, targeting normal cCa and phosphorus concentrations, avoiding symptoms of hypo- or hypercalcemia, and minimizing the extent of hypercalciuria. Oral calcium supplementation may be used as needed on top of a minimum daily dietary intake of at least 1000 mg. Participants previously treated with magnesium and potassium citrate supplements when not on CLTX-305 (encaleret) may not be restarted on treatment during LTE, if the blood magnesium and urine citrate are within the normal ranges during Period 3.

Study visits include inpatient or outpatient NIH CC visits every 6 months starting at Month 6 and telephone contacts along with outpatient laboratory assessments every 6 months starting at Month 3. Laboratory assessments will be performed every 3 months for evaluation of efficacy and safety. Laboratory assessments at the NIH CC will be collected approximately 4-hours post-AM CLTX-305 (encaleret) dose. AEs and concomitant medications will be recorded during these visits. Participants will be contacted by telephone per protocol at intervals during LTE to review the results of outpatient laboratory blood and urine assessments, confirm adequacy of the current regimen of study medication (including supplements), inquire about hypo/hypercalcemia symptoms, and assess for AEs. The LTE is designed to obtain additional long-term safety data for CLTX-305 (encaleret). Participants who elect to continue in LTE will receive CLTX-305 (encaleret) for an additional period of time, up to 25 months (approximately 2 years) or until they transition to the CLTX-305-302/CALIBRATE Phase 3 LTE, whichever occurs first.

For details on the visit schedule and activities in LTE see Section 1.3.

The total blood volume collected over approximately 25 months during LTE for each participant will be less than the blood volume limits per participant as per NIH Guidelines for Blood Draw Limits for Research Purposes (M95-9, June 2009). This includes the 4 inpatient or outpatient NIH CC visits.

Participants are considered to have completed the study once they complete 24 weeks of Period 3 and the safety follow-up visit. If a participant ends involvement in the study before completing the Period 3 activities, steps outlined in Schedule of Activities will be followed, see Section 1.3 Table C.

At any point during the LTE, and before transition to the CLTX-305-302/CALIBRATE Phase 3 LTE, participants can choose to stop participation and be placed back on the conventional therapy. Follow-up assessments are to be completed (see Section 1.3 Table D) and clinical supply of CLTX-305 (encaleret) needs to be returned to the investigative site.

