- Document current CLTX-305 (encaleret) dose and calcium dosing regimen, any modifications, and reason for modifications
- Outpatient laboratory testing: Blood samples for clinical laboratory panels (Na, Cl, bicarbonate, K, BUN, Cr and including Alb, Ca, Mg, PO4, iPTH, CTX, and P1NP).
-  Height measured only at month 24/final visit or ET visit
- Vital signs include supine or sitting blood pressure (BP) by automated cuff, heart rate (HR), and respiratory rate.
- Safety and Drug Monitoring Labs collected at the NIH CC visits approximately 4 hours after the morning encaleret dose Chemistry (Na, K, Cl, bicarbonate, Glu, BUN, Cr, Alb, total protein, Ca, Mg, PO4, iPTH, 25-OH Vitamin D, CTX, P1NP, Cholesterol, TG, AST, ALT, Tbili, Alk phos, LDH, amylase, lipase, uric acid, CK), Hematology (RBC, Hgb, Hct, RBC indices, WBC, diff), Coagulation (PT/PTT/INR), Research labs (FGF23 and mid-molecule PTH). HIV, viral hepatitis panel should be repeated within 3 months prior to transition to CLTX-305-302/CALIBRATE.
- 9 Blood β-HCG pregnancy test can be performed at the NIH CC on the day of transition to CLTX-305-302/CALIBRATE Phase 3 LTE, and an aliquot will also be sent to the central lab for the CLTX-305-302/CALIBRATE Phase 3 LTE.
-  CLTX-305 (encaleret) administered and recorded during the NIH CC visit/in-house days.
- Outpatient 24-hr urine collection for Ca, Mg, PO4, Cr, Na, K, citrate, pH
- A final follow-up safety telephone call and outpatient labs will occur 30 ± 7 days after the last dose of CLTX-305 (encaleret).
- 13 If a participant is not able to enter the LTE immediately following Period 3, then participant will be reconsented to and may restart CLTX-305 (encaleret) at the previous therapeutic dose determined in Period 3. Safety and Drug Monitoring Laboratory tests should be done while participant is at the NIH CC.
- When participant transitions to CLTX-305-302/CALIBRATE Phase 3 LTE, participant will be asked to return to the NIH CC to return the unused CLTX-305 (encaleret), and complete any remaining eligibility assessments for the CLTX-305-302/CALIBRATE Phase 3 LTE study.
- 15 If the Month 24 visit aligns with the transition to the CLTX-305-302/CALIBRATE Phase 3 LTE, then the renal ultrasound and DXA scan will be performed once as part of the CLTX-305-302/CALIBRATE Phase 3 LTE.

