CLTX-305 (encaleret) can cause hypercalcemia acutely, in healthy volunteers and postmenopausal women, at doses of 30 mg, with some additional effect at doses of 50 and 100 mg. At doses higher than 30 mg, the primary effect was to increase the duration of PTH and calcium elevation. Chronically, CLTX-305 (encaleret) doses of 7.5, 10 and 15 mg were associated with an increased propensity for hypercalcemia. Taken together these data from euparathyroid participants suggest that the steep portion of the dose-response curve for CLTX-305 (encaleret) effects on calcium concentrations occurs over approximately a one log range (10–100 mg) with a definitive efficacy to raise calcium acutely at 30 mg (for review of CLTX-305 (encaleret) dose-response for PTH, calcium and calcium-related hormones see Investigator Brochure).

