7.0 Study Objectives

This study is a single-site, open-label, dose-ranging study to evaluate the safety, tolerability and efficacy of CLTX-305 (encaleret) to maintain normalized albumin-corrected blood calcium (cCa) in subjects with hypocalcemia due to ADH1. The study consists of 2 cohorts, 3 periods and a Long-Term Extension (LTE) (Period 1, Period 2, Period 3 and Long-Term Extension [LTE]).

The **primary objectives** of this study are:

- Periods 1 and 2: Evaluate the safety and tolerability of single and multiple doses of CLTX-305 (encaleret) in subjects with ADH1.
- Period 3: Evaluate the safety, tolerability, and efficacy of CLTX-305 (encaleret) in subjects with ADH1 for 24 weeks.
- LTE: Evaluate the long-term (25 months or about 2 years) safety and tolerability of CLTX-305 (encaleret).

The **secondary objectives** of this study are:

Periods 1 and 2:

• Evaluate the effect of CLTX-305 (encaleret) to increase serum intact PTH (iPTH) levels after both single and multiple doses across a dose range in subjects with ADH1.

Periods 1, 2, and 3:

- Evaluate the PD effects of CLTX-305 on blood calcium concentrations.
- Evaluate the PD effects of CLTX-305 (encaleret) on associated measures of calcium. homeostasis including 1,25-(OH)₂ Vitamin D levels and urinary calcium excretion.
- Evaluate the PD effects of CLTX-305 (encaleret) on bone turnover markers including C-telopeptide (CTx) and procollagen type 1 N-propeptide (P1NP).
- Evaluate the PK of both single and multiple ascending doses of CLTX-305 (encaleret) in subjects with ADH1.

LTE:

- Obtain long-term data on efficacy to show durability of CLTX-305 (encaleret) on blood calcium concentrations.
- Evaluate the long-term PD effects of CLTX-305 (encaleret) on associated measures of mineral homeostasis including iPTH, 1,25-(OH)₂ Vitamin D levels and urinary calcium excretion.
- Evaluate the long-term effects of CLTX-305 on bone turnover markers including CTx and P1NP.

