13.3 Treatments

13.3.1 Extent of Study Drug Exposure

Exposure data will be summarized for Period 3 and LTE only using the Safety Analysis Set. The average daily dose for each period will be summarized for each period. The average daily dose will be derived as the sum of the dose levels times the number of days on each dose, divided by the number of days in the period considered. Additionally, the number of missed doses by period will be summarized.

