13.7.2 Secondary Analyses

The secondary efficacy endpoints at each visit and timepoints are presented in Table 6.

For each parameter in Table 6, absolute levels and change from baseline (where applicable) will be tabulated by visits, dose (for period 1 only) and timepoints (where relevant) and for each period separately. In addition, the mean ± SD and individual profiles for the absolute levels for selected parameters will be graphically presented by period, visits and timepoints (where relevant).

		Summary		
Specimen	Parameter	Absolute Value	Change from Baseline	Plots
	cCa levels			
	iPTH levels			
Blood	1,25-(OH) ₂ Vitamin D levels			
	eGFR levels			
	Albumin levels			
	Magnesium levels			
	Phosphorus levels			
	Creatinine levels			
	CTx levels		Period 1 only	
	P1NP levels		Period 1 only	
Urine	Fractional urinary calcium excretion			

Table 6: Efficacy/PD Parameters

		Sur	nmary	
Specimen	Parameter	Absolute Value	Change from Baseline	Plots
	Total urinary calcium excretion			
	Fractional urinary excretion for Magnesium			
	Tubular reabsorption of phosphate			
	Total urinary excretion for Magnesium			
	Total urinary excretion for Phosphate			
	Total urinary excretion for Sodium			
	Total urinary excretion for Potassium			
	Total urinary excretion for Citrate			
	Time-intervals and 24-hours levels for cAMP*		$\sqrt{**}$	
	Time-intervals for creatinine and pH			
	24 hours creatinine levels			
	24 hours pH levels			

* Not collected during the LTE.

** For Period 1 only.

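### In the LTE, encaleret dose and oral calcium can both be adjusted to hold cCa normal, but the visible SAP shows neither by visit, so the summary tables cannot separate a lasting effect from one maintained by more treatment.

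*Protocol*

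**What the plan says.** Participants enter the LTE on the dose established in Period 3 maintenance. Protocol 8.2.4 then says "CLTX-305 (encaleret) doses may be titrated as needed during LTE based on assessment of both blood and urine calcium results", and names the goals as "targeting normal cCa and phosphorus concentrations, avoiding symptoms of hypo- or hypercalcemia, and minimizing the extent of hypercalciuria". Section 6.1.6 has the same provision. A second adjustable treatment runs alongside: "Oral calcium supplementation may be used as needed on top of a minimum daily dietary intake of at least 1000 mg".

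SAP 7.0 gives the first LTE secondary objective as "Obtain long-term data on efficacy to show durability of CLTX-305 (encaleret) on blood calcium concentrations".

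For the analysis, SAP 13.7.2 says "absolute levels and change from baseline (where applicable) will be tabulated by visits, dose (for period 1 only) and timepoints", so dose is a table dimension in Period 1 only. SAP 11.1 presents LTE statistics by period and timepoint. On exposure, SAP 13.3.1 says "The average daily dose for each period will be summarized for each period", and adds the number of missed doses. The average is the sum of dose times days at that dose, divided by days in the period. SAP 10.1 takes the Period 2 baseline as the LTE baseline, so no visible LTE output is a change from Week 24. The paired tests in SAP 13.7.4 cover Periods 2 and 3 only.

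The data needed are recorded. Footnote 4 to the LTE schedule (Protocol 1.3, Table D) asks staff to "Document current CLTX-305 (encaleret) dose and calcium dosing regimen, any modifications, and reason for modifications". Table C has the same footnote for Period 3.

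**The concern.** When treatment is adjusted to hold a variable on target, that variable says little about whether the effect of a given treatment persists. The information moves into the amount of treatment needed. In the LTE, cCa is the controlled variable, and dose and oral calcium are the controls. Urinary calcium also guides titration.

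A stable mean cCa to Month 24 would therefore be compatible with three situations: a lasting effect on an unchanged regimen, a lessening effect offset by more encaleret or more calcium, and a growing effect accompanied by dose reductions. The durability objective needs these told apart. The visible tables give the controlled variable by visit and do not give the controls by visit.

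**Working it through.** The documents give no sample size, power or effect figure for the LTE, so there is no plan figure to reproduce. The check applies the SAP 13.3.1 formula to illustrative dose paths and asks what the planned exposure summary would reveal.

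**Inputs**
- LTE length: Month 24 target day 894 minus Week 24 target day 174 (SAP Tables 3 and 4) = 720 days.
- Period 3: about 12 weeks of titration and 12 of maintenance (Protocol 8.2.3), taken as 84 + 84 days.
- Dose range: 10 mg once daily to 180 mg BID in the first 7 participants to enter Period 3 (Protocol 8.2.2), that is 10 to 360 mg/day, a 36-fold span.
- Dose paths: my assumptions, kept inside that range.

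**1. Can one LTE average separate stable from changing dose?**
- Flat 120 mg/day: 120.
- 60 then 180, 360 days each: (60 × 360 + 180 × 360)/720 = 86,400/720 = 120.
- 180 then 60: also 120.

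It cannot.

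**2. Does comparison with the Period 3 average rescue it?** Not reliably, because that average includes titration.
- Period 3 at 360 then 120 mg/day: (360 × 84 + 120 × 84)/168 = 40,320/168 = 240.
- LTE at 120, 240, 360 mg/day for 240 days each: 172,800/720 = 240.

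The dose has tripled from its maintenance level and the two averages agree. The direction is plausible: Protocol 4.3 expects that chronic doses may be lower than acutely effective ones.

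**3. When does the comparison work?** If Period 3 was flat at 120 mg/day, the same LTE path gives 240 against 120, a ratio of 2.0. A large rise after a stable Period 3 would show.

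**4. What if only some participants need more?** Suppose 3 participants double from 120 mg/day at Month 12 and the others stay at 120. Each of the 3 averages (120 × 360 + 240 × 360)/720 = 180.
- n = 10 (5 + 5, the cohort minimums): (7 × 120 + 3 × 180)/10 = 138 mg/day.
- n = 16 (the planned maximum entering treatment): (13 × 120 + 3 × 180)/16 = 131.25 mg/day.

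At the low end of the range, one participant going from 10 to 30 mg/day for the whole LTE moves a 16-person mean by 20/16 = 1.25 mg/day. With a 36-fold spread between participants, a group mean in mg is insensitive to a change that is large for one person. A within-participant ratio is not.

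**5. Oral calcium.** SAP 13.3.1 covers study drug only. SAP 13.3.2 describes concomitant medication tables ordered by frequency of class and name, with no amount. A higher supplement dose in someone already taking calcium would not appear in such a table.

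**The case against.** The strongest reply is that the information is not hidden. SAP 13.0 lists all collected data by subject, and with at most 16 or so participants the dose histories can be read directly. The average daily dose will carry SD, quartiles, minimum and maximum as well as the mean, and step 3 shows that it can register a rise. Exact cancellation, as in step 2, needs a chosen path. This stands, and it limits the point to the summary tables. A listing still has to be turned into a summary before it can support a statement about durability.

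Second, the regimen under study is individualised titration without calcitriol, and whether that regimen keeps calcium normal over two years is a legitimate question. It is, and the planned tables answer it. The split proposed below adds a second answer and does not replace the first.

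Third, the SAP text available has gaps: 10.13, 10.15 and whatever lies between 13.7.2 and 13.7.4 cannot be read. The change history mentions responder endpoints that do not appear in the visible endpoint tables. A dose-related LTE output may exist there, so the statement of absence covers the visible text only.

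A reader might go further and infer that waning efficacy will be reported as durable. The documents do not support that. Nothing in them shows waning, and no section commits the sponsor to a durability conclusion from a flat mean. Protocol 2.2.2 reports no tachyphylaxis in iPTH response at 6 and 12 months, although in postmenopausal women on once-daily dosing.

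A reader might also try to convert a dose multiple into a percentage of lost response, because Protocol 2.1 says "the steep portion of the dose-response curve for CLTX-305 (encaleret) effects on calcium concentrations occurs over approximately a one log range". That describes the steep part of the curve in euparathyroid participants, and the same section says that above 30 mg the main effect was on duration. A log-linear response over exactly one log in ADH1 is not supported, so no such percentage is given.

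**Conclusion.** The point holds for the planned summary tables. LTE treatment is titrated on the efficacy variables, the visible efficacy tables carry no LTE dose, and the single LTE average is identical for flat, rising and falling paths. The tables therefore cannot show whether cCa was maintained on a stable regimen or by increasing encaleret or calcium.

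The size of any masking cannot be estimated from the documents. The figures above illustrate what the formula can conceal under assumed paths and do not predict what happened. Listings and period averages give partial visibility.

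This affects a secondary, descriptive objective reported in an addendum to the CSR. It leaves the LTE primary safety objective and the Period 3 efficacy results untouched. It is worth correcting because the correction is cheap and lets the LTE address its own objective.

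**What to change.** In SAP 13.3.1 and 13.7.2, add for each LTE analysis visit, beside cCa and 24-hour urinary calcium:
- total daily encaleret dose;
- its within-participant ratio to the Week 24 dose;
- daily calcium supplement dose.

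Then report the number of participants with cCa in the normal range, split into (a) those with neither dose nor supplement above the Week 24 level and (b) those with dose, supplement or both increased, giving the recorded reason. Interpret durability in light of that split. The reason matters because a supplement may be raised to make up low dietary intake and not to offset a weaker drug effect. State which reference range defines normal, since LTE results come from the NIH, local laboratories and, after transfer, a central laboratory.

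The cost is SAP wording and one table in the CSR addendum. Cell counts will be small. LTE data may sit partly in the CALIBRATE eCRF (Protocol 10.8.3, SAP 10.14), so dose and supplement fields there must be checked and mapped. Nothing here changes how doses or supplements are adjusted.

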# 8.2.5 Follow-up and Early Termination

Participants will receive a follow-up call  $30 \pm 7$  days after their last dose of the study medication for assessment of AEs.

If participants discontinue from taking part in the study or are terminated early from the study, they should have all safety assessments for Early Termination (ET) as listed in the Schedule of Activities (Section 1.3).

When a participant discontinues or withdraws from taking study medication, they will revert to their prior outpatient regimen of oral calcium and active Vitamin D to address their underlying ADH1 and maintain cCa blood concentrations as they return to their prior clinical care providers. Participants will be instructed to undergo outpatient laboratory testing of their blood calcium within 1–3 days of discontinuing study medication and to have those results sent to NIH investigators for review. Study investigator should contact the participants to review the blood calcium results and advise on optimizing their outpatient clinical management.

Participants who transfer to the CLTX-305-302/CALIBRATE Phase 3 LTE will continue encaleret dosing at their prescribed dose until enrolled into the CLTX-305-302/CALIBRATE Phase 3 LTE. When a participant transitions to CLTX-305-302/CALIBRATE Phase 3 LTE, participant will be asked to return to the NIH CC to return the unused CLTX-305 (encaleret), and complete any remaining eligibility assessments for the CLTX-305-302/CALIBRATE Phase 3 LTE study.

